Hypotheses. There are four hypotheses. They include the following:

- To examine whether the students in the HIV/STD intervention schools report less sexual risk behavior than do students in the control schools.
- To examine whether the intervention effects are significantly different among adolescents who vary in pre-intervention sexual experience, age, gender, intimate-partner violence, and sexual abuse history. This information would guide the development of future interventions tailored to subgroups of South African adolescents.
- To examine whether theoretically defined mediators of behavior change (that is, knowledge, behavioral beliefs, normative beliefs, perceived self-efficacy, and intentions) do indeed act as mediators of the intervention's effects on sexual risk behavior.
- To examine whether students in the HIV/STD intervention schools are less likely to test positive for a STD than are students in the control schools.

Statistical Power. Power analysis was performed to determine the sample size needed to detect effects of the interventions on self-reported frequency of unprotected sexual intercourse. We estimated the intracluster correlation coefficient from the pilot data we collected on 6th grade students at 4 schools in Mdantsane. The intracluster correlation for frequency of unprotected sexual intercourse was $\rho = 0.00864$. Assuming $\alpha = .05$, two-tailed, a total of 1,057 6th grade learners from the 18 schools in the trial with an average of 59 students in each school, the estimated power for tests of the effects of interventions on outcomes where the effect size is at least $d = 0.25$ is greater than 99% for attrition rates at the 12 month follow up of 15-20%.

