We also estimated statistical power for STD incidence specifically. Some of the participants will be sexually experienced at the time of the follow-ups and therefore at risk of STD, but others will not be sexually experienced and therefore not at risk for STD. The power analysis for STD incidence must take into account the size of sample that is at risk. The median age of first sexual intercourse in South Africa is about 16 (MacPhail et al., 2002; Manzini, 2001; Richter et al., 2005; Simbayi et al., 2004). At baseline 76.54% of the adolescents in our study were 12 years or older and therefore will be 16 years or older at the 54-month follow-up. We considered three different rates of sexual experience and risk for STD at the 54-month follow-up: 76.5% (N=809), 51.3% (N=542), and 38.3% (N=405) of the original 1,057 participants.

Based on previous studies (Auvert et al., 2001; Johnson et al., 2005), we estimated that about 15.4% of the sexually experienced participants in the absence of a HIV/STD risk-reduction intervention would test positive for CT, GC, or TV at either the 42-month or the 54-month follow-up. We estimated power for detecting significant differences in STD incidence over the follow-up period for attrition rates of 15% and 20% at the 54-month follow-up, $\rho = 0.009$, and STD incidence in the health-promotion control group = 0.154. At baseline, only 3.3% of participants were sexually experienced; hence, for the other 96% of participants, any STDs we detect will have been contracted during the follow-up period. The study is well powered to detect incidence differences in the range of at least 6.4% to 8.4%, depending on the true proportion of sexually experienced adolescents in the sample at the 54-month follow-up. Table 1 presents a range of estimates based on 38.3% to 76.5% of the baseline sample contributing to the STI incidence endpoint at the 54-month follow-up.

Table 1. Estimated power to detect a decrease in STD incidence assuming a cluster randomized controlled trial with a total of N=809, N=542, and N=405 sexually experienced participants enrolled from 18 matched pairs of schools (alpha = 0.05, two-tailed, rho = 0.009).

STD incidence			Attrition rate (54 months)					
			20%			15%		
Control	Intervention	Difference	N=809	N=542	N=405	N=809	N=542	N=405
0.154	0.10	0.054	0.76	0.58	0.47	0.78	0.61	0.49
0.154	0.09	0.064	0.88	0.73	0.60	0.90	0.75	0.63
0.154	0.08	0.074	0.95	0.84	0.72	0.96	0.86	0.74
0.154	0.07	0.084	0.98	0.91	0.81	0.99	0.93	0.84

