
Statistical Analyses. To address Hypothesis 1, we will use intervention type as the independent variable and model the incidence of sexual intercourse, unprotected sexual intercourse, and multiple partners as binary responses to test the effect of intervention using GEE on data collected preintervention and 3-, 6-, 12-, 42-, and 54-month follow-up.

Hypothesis 2 concerns whether the effects of HIV risk-reduction interventions may differ systematically among adolescents. Sexual experience, age, gender, intimate-partner violence, and sexual abuse history are the primary moderators of responsiveness to the HIV risk-reduction intervention we will consider. Although the notion that certain variables may moderate intervention effects is theoretically persuasive, little research has attempted to establish empirically the characteristics of intervention participants that might moderate the effectiveness of HIV risk-reduction interventions. Jemmott et al. (1998) found that a safer sex intervention was more efficacious with sexually inexperienced adolescents. We will test moderator effects using GEE, along the guidelines described by Baron and Kenny (1986) and Cohen and Cohen (1983). We will use GEE to test for significant interactions between intervention type and potential moderator, controlling for the main effects of all variables involved in the interaction. As an example, consider the moderation of intervention effects on intentions by age assessed as a continuous variable. By introducing an age-by-intervention interaction term, this moderation effect is easily tested using GEE.

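### The Hypothesis 1 power statement is for a frequency of unprotected intercourse, but Hypothesis 1 is tested on three binary outcomes for which no power basis is given

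*Protocol*

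**What the plan says.** Section 1 of the protocol, under Statistical Power, says the calculation was done to "detect effects of the interventions on self-reported frequency of unprotected sexual intercourse". The inputs are 1,057 learners in 18 schools (about 59 per school), two-sided alpha 0.05, and an intracluster correlation of 0.00864 estimated for that same frequency in pilot data from 4 schools. The claim is that power where "the effect size is at least $d = 0.25$ is greater than 99" per cent, for "attrition rates at the 12 month follow up of 15-20" per cent.

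The same section, under Statistical Analyses, says that for Hypothesis 1 the investigators will "model the incidence of sexual intercourse, unprotected sexual intercourse, and multiple partners as binary responses to test the effect of intervention using GEE", on data from before the intervention and from 3, 6, 12, 42 and 54 months.

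On how common these outcomes are, the text on power for STD incidence says "At baseline, only 3.3% of participants were sexually experienced". It then considers 38.3%, 51.3% and 76.5% sexually experienced at 54 months. For STD incidence, which Hypothesis 4 tests, the protocol does give a control rate (0.154), intervention rates, an intracluster correlation and a power table.

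**The concern.** The variable used for power is not among the outcomes that Hypothesis 1 tests. A standardised difference in a frequency has no fixed meaning for a yes/no outcome. Power for a proportion depends on the control rate, the target difference and the intracluster correlation of the binary variable, and the protocol gives none of these for intercourse, unprotected intercourse or multiple partners.

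The risk lies in interpretation. A reader told that power exceeds 99% would take a non-significant binary result as good evidence of no effect. The mediation plan under Hypothesis 3 also intends to interpret non-significant behavioural effects, so realistic power matters there too.

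**Working it through.** **Inputs from the protocol.** 1,057 learners; 18 schools in matched pairs, hence 9 per arm; rho = 0.00864; two-sided alpha 0.05; attrition 15% to 20%.

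**Step 1: the plan's own figure, for a continuous outcome.** Design effect DE = 1 + (m − 1) × rho, where m is the retained number per school. Effective n per arm = retained total / (2 × DE). Power = Φ(d × √(n/2) − 1.96).

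| Attrition | Retained | m | DE | Effective n per arm | d√(n/2) | Power |
|---|---|---|---|---|---|---|
| 15% | 898.4 | 49.9 | 1.423 | 315.8 | 3.141 | 0.881 |
| 20% | 845.6 | 47.0 | 1.397 | 302.6 | 3.075 | 0.868 |

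The claim of more than 99% is not reproduced. Ignoring clustering altogether gives 96.3% and 95.3%. Averaging three follow-ups gives 91% to 97%. Counting 1,057 learners in 18 schools for each arm gives 99.4% and 99.2%. On the stated design, 99% power needs d of about 0.34 to 0.35.

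**Step 2: power for a binary outcome at 12 months.** The control rates of 5%, 10% and 20% are assumptions. The protocol gives none for this visit, and the only observed cohort rate is the 3.3% sexually experienced at baseline. The intracluster correlation of the frequency is borrowed because no binary one is given. With 20% attrition, n = 302.6 per arm, SE = √[(p1(1 − p1) + p2(1 − p2)) / n] and power = Φ((p1 − p2)/SE − 1.96).

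| Control rate p1 | p2, 30% reduction | Power | p2, 50% reduction | Power |
|---|---|---|---|---|
| 5% | 3.5% | 0.15 | 2.5% | 0.37 |
| 10% | 7.0% | 0.26 | 5.0% | 0.65 |
| 20% | 14.0% | 0.50 | 10.0% | 0.94 |

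Worked line for 10% falling to 7%: SE = √[(0.0900 + 0.0651)/302.6] = 0.0226; 0.030/0.0226 = 1.325; Φ(1.325 − 1.96) = 0.26.

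**Step 3: the same calculation for intercourse at 54 months.** The control rates are the protocol's own scenarios for sexual experience, with the same design and 20% attrition. Power for a 30% relative reduction is 0.86 at 38.3%, 0.97 at 51.3% and above 0.99 at 76.5%.

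**Step 4: the less common outcomes at 54 months, as an illustration.** The Background section cites a national survey in which 41% of sexually experienced adolescents did not always use condoms and 18% had multiple partners. If those fractions held in this cohort, unprotected intercourse would be about 16% to 31% (0.383 × 0.41 to 0.765 × 0.41) and multiple partners about 7% to 14% (0.383 × 0.18 to 0.765 × 0.18). Power for a 30% reduction would then be about 0.40 to 0.75 and 0.19 to 0.35.

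**The case against.** **The claim is worded for any outcome with d of at least 0.25.** It is, but without a control rate that wording cannot be applied to a yes/no outcome, and the conversion matters. On the arcsine scale, d = 0.25 at control rates of 5%, 10% and 20% is a relative reduction of 80%, 62% and 45%. On the logit scale (odds ratio exp(−0.25π/√3) = 0.635) it is about one third, and power for that effect is 19% to 20% at a 5% control rate and 33% to 34% at 10%. A reader might infer that the protocol assumes implausibly large effects. The documents do not support this. The size depends on the conversion, the protocol sets no limit of plausibility, and its STD table plans on falls from 0.154 to between 0.10 and 0.07, which are reductions of 35% to 55%.

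**The outcomes are not rare throughout.** This stands. Low rates are documented only at baseline, and the model runs to 54 months, where d = 0.25 on the arcsine scale is only a 15% to 30% reduction in intercourse.

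**The GEE uses repeated visits.** This also stands. The power figures above are for a single visit, and repeated measures may raise power somewhat.

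**The protocol does power a binary outcome.** It does, for STD incidence under Hypothesis 4. It would be wrong to say that no tested outcome has a power calculation; the gap is confined to Hypothesis 1.

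**Conclusion.** The point holds in this form: the stated power of more than 99% does not apply to the Hypothesis 1 tests, and nothing in the protocol supplies the inputs needed to work out the power that does. For a 30% reduction at 12 months, power is about 0.15 to 0.50 over assumed control rates of 5% to 20%. At 54 months it is 0.86 or more for intercourse. The shortfall therefore concerns the early visits and the less common outcomes.

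A reader might infer that the trial is underpowered for Hypothesis 1 as a whole, or that its main test fails. The documents do not go that far: they name no single visit or binary contrast as the main test, and power varies widely by outcome and visit. The binary figures rest on assumed 12-month rates, an intracluster correlation borrowed from the frequency variable, single-visit comparisons, and reductions of 30% and 50% chosen as benchmarks. The finding that the stated inputs give about 87% to 88% for a continuous outcome needs no assumed rate, only the standard design-effect calculation.

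**What to change.** Replace the statement of more than 99% with power for each of the three binary Hypothesis 1 outcomes at 12 and 54 months. For each, state control-rate scenarios, a target reduction, 9 schools per arm, the attrition assumed, and an intracluster correlation for the binary variable from the existing pilot data. As that pilot covered only 4 schools, a stated range for the correlation would also serve. If credit is taken for repeated visits, give the assumed within-person correlation.

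The cost is a recalculation and a rewritten paragraph, with no change to the design. The drawback is that the stated power will be less favourable for the less common outcomes and the early visits.

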Hypothesis 3 concerns mediation of intervention effects. The theoretical framework underlying the intervention suggests that knowledge, perceived self-efficacy, behavioral beliefs, normative beliefs, and intentions should mediate the effects of the intervention on sexual-risk behavior. Mediation will be tested using a standard procedure described by Baron and Kenny (1986). To establish mediation, it is necessary to show that (a) the independent variable affects the dependent variable; (b) the independent variable affects the putative mediator; and (c) the mediator has a significant effect on the dependent variable when the independent variable is controlled. Within our context, the analyses will proceed as follows: we will test for statistical significance of the intervention's effect on sexual behavior. We will then test the effect on the potential mediators. Finally, we will test whether the potential mediators have significant effects on sexual behavior, controlling for intervention effects. This set of analyses will indicate whether the 3 criteria of mediation are met. If the intervention effect on sexual behavior outcomes is nonsignificant, these analyses would provide valuable information as to whether a

lack of effects on mediators may account for it. In addition, the analyses would establish whether the changes in the mediators predict reduced risk behavior, even if the intervention effects are nonsignificant. In this way, it will be possible not only to gain insight into the underlying mechanisms of behavior change, but also to test the theoretical framework that was used to guide the creation of the interventions.

To address Hypothesis 4, we will use intervention type as the independent variable and model the incidence of STD as binary response to test the effect of intervention using GEE on data collected at the 42- and 54-month follow-up.

2. Duration

Funded by the National Institute of Mental Health

Start date: April 1, 2002

End date: August 31, 2010

3. Subject Recruitment and Selection

The participants will be 1,057 6th grade Xhosa speaking South African adolescents recruited from 18 senior primary schools in Mdantsane and Berlin, Eastern Cape Province, South Africa. About 59 participants will be recruited from each of the 18 schools. On average, participants will range in age from 11 years to 14 years at baseline. About one-half of the adolescents will be female.

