Parent/Guardian Focus Groups. We will conduct 3 focus groups with parents or guardians of adolescents: an all-female group, an all-male group, and a mixed-gender group. Each group will involve approximately 10 participants. The purpose is to solicit parent/guardians' input regarding the adolescents' behaviors we seek to change.

Pilot Testing the Questionnaire and Interventions. We will pilot test the revised questionnaire with 20 6th grade students in Mdantsane. We will then pilot test the interventions with 30 6th grade adolescents at a school in Mdantsane. One-half of the students will be randomly assigned to receive the HIV/STD sexual risk reduction intervention and, the others, to receive the general health-promotion control intervention.

The pilot participants will complete the pre-intervention questionnaire and then receive their intervention in 6 2-hour weekly sessions. They will subsequently complete the post intervention questionnaire. We will debrief the participants to solicit their comments regarding how we might improve the project. We will use this experience to make final revisions to the intervention and questionnaires.

Intervention Design. The design of the study is a randomized controlled trial. The schools will be randomly assigned to receive either the HIV/STD risk-reduction intervention or the general health-promotion control intervention. The study will be held during the extracurricular activity period at 18 schools in Mdantsane and Berlin, South Africa. The intervention will be conducted in Xhosa and will consist of 6 2-hour sessions.

On a day before the first session of the intervention, all adolescents will complete a Xhosa pre-intervention questionnaire measures. After completing the questionnaires, adolescents will attend the first intervention session, which will be implemented by specially trained Xhosa speaking male and female co-facilitators. The intervention will be implemented over 6 sessions.

Intervention Type has 2 levels:

- HIV/STD risk-reduction intervention consisting of 12 1-hour modules over 6 sessions,

- General health-promotion control intervention consisting of 12 1-hour modules over 6-sessions, which serves as a control group.

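### The Hypothesis 1 GEE lists the preintervention visit among its data with intervention type as the only named predictor; if run as written with the intervention main effect tested, the estimate is attenuated toward the null, probably by about 5%

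*Protocol*

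**What the plan says.** Protocol section 1 (Purpose), under Statistical Analyses, sets out the Hypothesis 1 model in one sentence. On predictor and outcomes: "we will use intervention type as the independent variable and model the incidence of sexual intercourse, unprotected sexual intercourse, and multiple partners as binary responses". On data: "to test the effect of intervention using GEE on data collected preintervention and 3-, 6-, 12-, 42-, and 54-month follow-up". Preintervention heads a single list with the five follow-ups. Nothing there says whether its value is a response or a covariate, and nothing says which coefficient is the test.

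Three other places bear on how to read it.
- Section 6 (Research Design) fixes the timing of the baseline measure: "On a day before the first session of the intervention, all adolescents will complete a Xhosa pre-intervention questionnaire measures".
- The Hypothesis 4 sentence has the same construction, with intervention type as predictor and a binary response, and plans to "test the effect of intervention using GEE on data collected at the 42- and 54-month follow-up".
- Where the protocol wants further model terms it can name them. For Hypothesis 2: "We will use GEE to test for significant interactions between intervention type and potential moderator, controlling for the main effects of all variables".

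**The concern.** On its plain reading the sentence makes the preintervention behaviour one of six repeated responses and tests a single intervention term. At that visit neither arm has received anything, so the expected difference is zero. A pooled intervention coefficient is then a weighted average of five follow-up effects and one structural zero, and any chance baseline difference between arms enters the estimate instead of being adjusted out.

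The Hypothesis 4 sentence supports this reading. STD specimens are taken only at 42 and 54 months, so its list of visits can only mean response occasions, and the parallel phrase in Hypothesis 1 naturally means the same.

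What is at stake is power for the main behavioural question. The mediation analysis (Hypothesis 3) is also affected, because it begins by testing the intervention effect on sexual behaviour.

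**Working it through.** **Stated inputs.** Six visits enter the Hypothesis 1 GEE. The true effect at the preintervention visit is 0. Section 1, Statistical Power, gives for baseline: "At baseline, only 3.3% of participants were sexually experienced". It also gives 18 schools, 1,057 learners, an average of 59 per school, an intracluster correlation of 0.00864, and three planning rates of sexual experience at 54 months (76.5%, 51.3%, 38.3%).

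**Assumed inputs.** Prevalences at the other visits, within-person correlation, and attrition by visit.

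**The plan's own figure.** The protocol gives no figure for attenuation. The nearest is power above 99% for d = 0.25. From the stated inputs with 15% attrition: 1,057 × 0.85 / 2 = 449.2 per arm; design effect 1 + (49.9 − 1) × 0.00864 = 1.423; effective 315.8 per arm; power Φ(0.25 × √(315.8/2) − 1.96) = 0.88. With 20% attrition it is 0.87. The stated figure does not reproduce, but that is a separate matter and nothing below depends on it.

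**Step 1: weight of the baseline visit.** In a logistic model with working independence, a visit's information is roughly proportional to p(1 − p). If the follow-up effect is constant, the proportional attenuation equals the baseline visit's share of the total.

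| Prevalence at 0, 3, 6, 12, 42, 54 months | Sum of p(1 − p) | Baseline share |
|---|---|---|
| 0.033, 0.05, 0.06, 0.10, 0.35, 0.45 | 0.7008 | 0.0319 / 0.7008 = 0.046 |
| 0.033, 0.04, 0.045, 0.06, 0.20, 0.30 | 0.5397 | 0.0319 / 0.5397 = 0.059 |
| all visits equally informative | n/a | 1/6 = 0.167 |

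Putting the protocol's lowest and highest planning rates at 54 months into the first profile gives 0.0319 / 0.6896 = 0.046 (38.3%) and 0.0319 / 0.6331 = 0.050 (76.5%).

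**Step 2: effect on power.** Take a test with 80% power (standardised effect 2.80, two-sided 5%) and leave the standard error unchanged.
- 4.6% attenuation: Φ(2.80 × 0.954 − 1.96) = Φ(0.711) = 0.76.
- 5.9%: Φ(2.80 × 0.941 − 1.96) = Φ(0.675) = 0.75.
- 16.7%: Φ(2.80 × 0.833 − 1.96) = Φ(0.372) = 0.645.

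**Step 3: check on the odds-ratio scale.** Expected estimates came from a logistic model with visit terms, working independence and assumed attrition, with baseline among the responses. A true follow-up odds ratio of 0.50 is estimated as 0.52 if prevalence rises to about 50%, 0.55 if it rises to 10%, and 0.59 if it stays at 3.3%. With follow-ups only as responses it is 0.50. On the log scale 0.521 is an attenuation of 1 − ln(0.521)/ln(0.50) = 5.9%, in line with step 1. The flat case exceeds one sixth because attrition and the effect itself leave each follow-up with less information than baseline; a flat 3.3% does not fit the protocol's planning rates.

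**Step 4: the equal-weight extreme.** On a standardised-mean scale, d = 0.25 becomes 0.25 × 5/6 = 0.208. At 20% attrition the effective n is 302.6 per arm, and the variance of a K-visit mean is (1 + (K − 1)r)/K.

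| Within-person r (assumed) | Six visits, d = 0.208 | Five follow-ups, d = 0.25 |
|---|---|---|
| 0.2 | 0.993 | 0.999 |
| 0.4 | 0.952 | 0.989 |
| 0.6 | 0.881 | 0.962 |
| 0.8 | 0.802 | 0.919 |

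**Step 5: chance baseline imbalance.** Ignoring the matching and borrowing the stated intracluster correlation, the design effect is 1 + 58 × 0.00864 = 1.501. The standard error of a baseline difference is √(2 × 0.033 × 0.967 × 1.501 / 528.5) = 0.0135, or 0.0135 / 0.0319 = 0.42 in log-odds. At 5% weight this adds about 0.02 log-odds to the pooled estimate.

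**The case against.** The strongest reply is that the sentence lists the data used and does not fully specify a model. Preintervention data are also used in a baseline-adjusted GEE and in a repeated-measures GEE that tests intervention by time, and neither dilutes the effect. Covariates, visit terms and contrasts are commonly left to an SAP, which is not shown, and this document is an IRB summary. The word incidence also fits behaviour after baseline better than a baseline response. All of this stands against any claim that the analysis will be diluted, and it is why the point is conditional. It does not remove the point: the harmless models are not written, and the one that is written is weaker than an equally cheap alternative.

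The Hypothesis 4 comparison is also limited. That list omits baseline because no specimens exist then, not because its authors treated baseline differently. It supports the reading of the list as response occasions and no more.

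Three stronger readings are tempting, and the documents do not support them.
- **A loss of one sixth, or power near 64%.** This needs equal information at every visit, or an analysis stopping at 12 months (baseline share 0.174 with assumed prevalences 0.033, 0.04, 0.05, 0.07). The Hypothesis 1 sentence runs to 54 months, and baseline experience is only 3.3%.
- **Serious distortion from baseline imbalance with nine schools per arm.** Schools are matched in pairs, rural and urban separately, and step 5 shows a contribution of about 0.02 log-odds.
- **Substantial precision thrown away.** A binary baseline at 3.3% can explain at most 0.033 × (1 − q) / (q × 0.967) of the variance of an outcome with prevalence q: 5.5% at 38.3% and 4.2% at 45%. More is possible at the early, low-prevalence visits.

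**Conclusion.** The point holds conditionally. If the Hypothesis 1 GEE is run as written and the intervention main effect is tested, the estimate includes a visit at which no effect can exist and is attenuated toward the null. The likely size is about 5 to 6%, taking 80% power to about 75 to 76%; about 17% is reached only with equally informative visits. The expected bias costs power and does not inflate false positives on average.

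These sizes rest on assumed follow-up prevalences, a constant follow-up effect, working independence and, for the power figures, an unchanged standard error. The 80% starting point is illustrative; the protocol claims more. The 3.3% refers to sexual experience in general. Unprotected intercourse and multiple partners must be rarer at baseline, but will also be rarer at follow-up, so their baseline shares cannot be fixed from the document.

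A reader might infer that the trial's main analysis is invalid or certain to be diluted. The text does not go that far, since it excludes neither a baseline covariate nor an intervention-by-time test. It is a modest improvement worth making because it is free.

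**What to change.** Amend the Hypothesis 1 sentence to state that the 3-, 6-, 12-, 42- and 54-month values are the responses, that the preintervention value of the same behaviour and visit are covariates, and that the intervention term is the test.

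If preintervention is to remain a response, state instead that the model includes visit and intervention-by-time terms, and that the test is the intervention-by-time contrast of follow-up against baseline.

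Either version removes the dilution and settles before analysis which coefficient answers Hypothesis 1. Adding age and gender as covariates is optional and not needed for this point. The cost is one sentence; no new data are required, because the preintervention questionnaire is already collected.

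### Hypothesis 3 makes a significant total effect on behaviour a condition for concluding mediation, which costs power without need

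*Protocol*

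**What the plan says.** Protocol section 1, Statistical Analyses, Hypothesis 3, adopts a three-step causal procedure. The governing sentence is "To establish mediation, it is necessary to show that (a) the independent variable affects the dependent variable". It goes on to require (b) an effect of intervention on the mediator and (c) a significant effect of the mediator on behaviour with intervention controlled. Criterion (a) is applied as a test of statistical significance. The decision is stated as: "This set of analyses will indicate whether the 3 criteria of mediation are met".

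The same paragraph provides for a nonsignificant total effect. The mediator analyses are still run, to see whether failure to move the mediators explains the null result and whether changes in the mediators predict behaviour. It does not say that mediation may then be concluded. No product of paths, indirect-effect estimate or interval is named.

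Two other places matter. The Statistical Power paragraph plans for an effect of at least d = 0.25 on outcomes, for "a total of 1,057 6th grade learners from the 18 schools in the trial". The Hypothesis 1 paragraph models the behaviours as binary responses by GEE on baseline and 3-, 6-, 12-, 42- and 54-month data.

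**The concern.** When an intervention works through a mediator, its total effect on behaviour is the intervention-to-mediator path times the mediator-to-behaviour path, plus any direct effect. The product is usually smaller than either path, so criterion (a) is usually the hardest of the three to meet. Making it compulsory means that a trial with clear evidence on both paths, but a total effect just short of significance, must report that the criteria are not met.

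Mediation is one of four stated hypotheses, and the protocol wants it to test the theory behind the intervention. An avoidable loss of power bears directly on that aim. This is also more than detail left for an analysis plan: a plan that concluded mediation without criterion (a) would contradict the word that makes it necessary.

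**Working it through.** **1. Power for criterion (a) at the protocol's own effect size.** Inputs from Statistical Power: 1,057 learners, 18 schools, ICC 0.00864, two-sided 0.05, d = 0.25, attrition 15-20%.

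- At 20% attrition: 1,057 × 0.80 = 845.6 learners, or 47.0 per school.
- Design effect = 1 + (47.0 − 1) × 0.00864 = 1.397. Effective n = 845.6 / 1.397 = 605, about 302.6 per arm.
- z = 0.25 × √(302.6 / 2) = 3.075. Power = Φ(3.075 − 1.96) = 86.8%. At 15% attrition it is 88.1%. With t on 16 df the figures are 82.3% and 83.9%.

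The protocol states that power "is greater than 99% for attrition rates at the 12 month follow up of 15-20" per cent. The stated inputs do not reproduce this, which is a separate matter. For the present point, criterion (a) passes in roughly 82-88% of trials at d = 0.25 on a continuous outcome. It falls to 50% at d = 1.96 / √(302.6 / 2) = 0.159.

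**2. Continuous outcome, simulated.** 2,000 runs per setting at effective n = 605. The documents give no path sizes, so the paths below (in SD units) are assumptions.

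| Intervention→mediator | Mediator→behaviour | Total effect | All three criteria | (b) and (c) jointly |
|---|---|---|---|---|
| 0.3 | 0.2 | 0.06 | 11% | 96% |
| 0.3 | 0.3 | 0.09 | 21% | 96% |
| 0.5 | 0.2 | 0.10 | 24% | 99.8% |
| 0.5 | 0.3 | 0.15 | 45% | 100% |
| 0.5 | 0.5 | 0.25 | 85% | 100% |

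These rows have no direct effect. With the direct effect set so that the total stays at 0.25, across paths of 0.3-0.8 and 0.2-0.5, the figures are 83-88% against 96-100%.

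**3. Binary outcome, total effect near d = 0.25.** On the log-odds scale this is 0.25 × π / √3 = 0.453. Simulated with 18 schools of 47, ICC 0.00864, school-clustered standard errors, t(16) and one follow-up, with the outcome at 10-20%, the rule succeeds in about 49-65% of trials. The joint test succeeds in 99-100%.

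A closed-form check of criterion (a) alone uses SE = √{1.397 × [p(1−p) + q(1−q)] / 423}:

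- Control 20%, intervention 13.7%: SE 0.0303, z = 2.08, power 50% (t) to 55% (normal).
- Control 10%, intervention 6.6%: SE 0.0224, z = 1.52, power 30-33%.
- If 20% is the lower of the two rates (28.2% against 20%): SE 0.0346, z = 2.38, power 61-66%.
- If 10% is the lower rate (14.9% against 10%): SE 0.0268, z = 1.82, power 40-45%.

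The simulated range therefore depends on which arm has the stated rate. Its lower end is optimistic if 10% is the control rate and the intervention lowers it.

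**4. Smaller total effect.** Take a mediator shift of 0.25 SD, log-odds 0.4 per SD of mediator, no direct effect and a 20% outcome. The total is 0.25 × 0.4 = 0.10 log-odds, or 0.10 × √3 / π = 0.055 SD. The rule succeeds in about 7% of trials and the joint test in about 84%. At a 5% outcome rate with the same paths the joint test also weakens: 3% against 57%.

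**5. Error rate.** With no intervention effect on the mediator, the joint test and a product-of-paths interval err in 4.8% and 4.6% of runs, and the three-criteria rule in 0%. This covers one mediator, one behaviour and no mediator-outcome confounding.

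**The case against.** A reader might infer that real mediation will usually be declared absent. The documents do not support that. The protocol places d = 0.25 on outcomes, and at that size the rule succeeds in most trials on a continuous outcome and in about half or more of the simulated trials on a binary one. The 7% figure arises when 0.25 is placed on the mediator, which makes the behavioural effect less than a quarter of the planned one.

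A reader might also infer that the indirect path goes unexamined, or that its size will never be reported. Criteria (b) and (c) test both component paths and are run even when (a) fails. An estimator and interval could sit in an analysis plan that is not at hand.

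Three further points have weight:

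- The simulations use one follow-up, while the protocol's GEE uses several. If pooling cut individual-level variance to 0.44-0.6 of its single-wave value (an assumption), criterion (a) at a 20% rate would pass in about 63-76% of trials.
- Hypothesis 3 asks about mediators of the intervention's effects on behaviour, so requiring such an effect is conservative rather than incoherent.
- Dropping (a) does not hold 5% error over the whole family of mediators and behaviours.

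All of this limits the size of the loss and shapes the fix. The necessity rule remains: the fallback produces the evidence but does not let it count as mediation.

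**Conclusion.** The point stands as an avoidable loss of power written into the decision rule. At the planned effect size the loss is modest on a continuous outcome and substantial on an uncommon binary outcome at a single follow-up. It becomes severe only if the true total effect is well below plan. On the effective-sample calculation, misses become the majority below about d = 0.16 for a continuous outcome. For a binary outcome that point can be reached at d = 0.25 itself when the control rate is near 10%.

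The direction is firm, because adding a required test cannot raise the chance of concluding mediation. The exact percentages are not firm. They rest on assumed path strengths and outcome rates and on a single wave, and the 99-100% for the joint test needs reasonably strong paths. The point warrants a change of wording and does not call the trial's main comparison into question.

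**What to change.** In the Hypothesis 3 paragraph:

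- Remove criterion (a) as a necessary condition and report the total effect descriptively beside the mediation results.
- For each mediator, estimate the indirect effect with a 95% interval that respects school clustering, either a Monte Carlo interval for the product of paths from school-robust standard errors or a school-level bootstrap. Conclude mediation when the interval excludes zero.
- Add a multiplicity statement. Five mediators and three behaviours make 15 pairs. At 5% each, up to 15 × 0.05 = 0.75 false claims would be expected if no pair were mediated.
- State that the mediator-to-behaviour path is not randomised. Adjust for baseline mediator and baseline behaviour, and state the no-confounding assumption.

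The cost is protocol or analysis-plan wording and a few lines of code, with no new data. What is given up is the near-zero false-positive rate of the three-step rule, replaced by about 5% per mediator-behaviour pair.
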